2.0 BACKGROUND

Although the long-term relapse-free survival (RFS) for most patients with low-risk Stage I and II melanoma is excellent following surgery, patients who have high-risk features such as tumor-involved lymph nodes (Stage III) have poorer outcomes with an average 5-year OS in Stage III patients of approximately 50%. (1) Modern therapy has significantly improved outcomes for patients with Stage IV melanoma such that 20% of patients are alive beyond 4 years or longer after diagnosis, but this still reflects a minority of patients. (2) Furthermore, relapses in this disease can be severely detrimental to quality of life with distant relapses accounting for greater than 50% of the relapse events in Stage III patients. (3) Adjuvant therapy is currently considered for patients with Stage III melanoma and selected patients with resected Stage IV melanoma.

Treatment with anti-programmed death-1 (PD-1) antibody induces significant response rates and durable survival in patients with metastatic melanoma. (4,5,6) Historically, adjuvant therapy for melanoma typically involves treatment with either high-dose interferon or high-dose ipilimumab. (7,8) But the role of PD-1 has moved to the forefront of adjuvant therapy with the results of CheckMate-238. (9) At this time, we are not able to predict which patients will derive benefit from adjuvant therapy and be long-term survivors (or cured). However, there is a need to identify patient or tumor characteristics that can distinguish those who will benefit from the cost, side effects, and time commitment of adjuvant treatment from those who will not.

While adequate and effective surgery is the goal of early treatment of primary melanoma, some cases with bulky nodal involvement are at high risk of local or distant recurrence despite upfront surgical resection. Neoadjuvant treatment offers the benefit of an early on-treatment pathological sample that can be profiled for additional biomarkers and correlated with survival. Additionally, treating with anti-PD1 antibody while tumor transiently remains in the body may generate a stronger

immune response against *in vivo* tumor antigens compared to the traditional adjuvant setting where tumor antigen is presented by microscopic residual tumor burden.

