6.0 STRATIFICATION FACTORS

Participants will be randomized between the Adjuvant arm and the Neoadjuvant arm in a 1:1 fashion, using dynamic balancing. Stratification will be based on:

1. Baseline LDH: Low/Normal (\leq institutional upper limit of normal) versus High ($>$ institutional upper limit of normal) and
2. Stage of disease at randomization: IIIB* versus IIIC* versus IIID*/IV

*Note: **Based on clinical staging as outlined in [Section 4.0](#)**. Participants who have only clinically occult lymph nodes, i.e. N1a-N3a, are not eligible.

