11.2 Analysis plan and sample size justification for primary objective

Based on EFS trends in this participant population, we will use exponential-mixture cure models to describe EFS patterns in the arms. Based on Weber 2017, we assume that on the adjuvant pembrolizumab (MK-3475) arm (null hypothesis) 60% participants will be long-term survivors (or cured or not observed to have an event during the finite follow-up of the trial) and that median EFS for participants who are not long-term survivors will be 2 years. We power this study to detect an alternative EFS in the neoadjuvant arm with 70% of participants being long-term survivors and median EFS among those who are not long-term survivors of 2.5 years. We note that these survival patterns do not follow a proportional hazards assumption and that average hazard ratios from Cox models are expected to become more null with additional follow-up.

We assume 1:1 randomization, accrual over 2 years, and up to 10 years of follow-up after randomization. Under these assumptions the average hazard ratio under the alternative is 0.64. Under the alternative, with a sample size of 500 eligible participants (250/arm), 100% of expected events is 104 events across both arms. At 50% of expected events (51 events, expected approximately when accrual completes), we will perform a futility test testing the alternative hazard ratio from a Cox regression model at the one-sided 2.5% level. No formal interim test of efficacy will be performed. Under the null hypothesis the probability of stopping early for futility is 45% and under the alternative is 2%. The final analysis will consist of a log-rank test of the null hypothesis at the two-sided 15% level (expected 1.5 years after accrual completes). The power of this design is 81%.

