11.4 Secondary endpoints and analyses

OS, local/regional control, and disease control will be estimated using the Kaplan-Meier method and compared between arms using log-rank tests and Cox regression models. Fisher's exact test will be used to compare the number of pembrolizumab (MK-3475) doses received by participants on each treatment arm. Pathologic response, RECIST 1.1

response rates, iRECIST response rates will be tabulated for the neoadjuvant arm and exact 95% confidence intervals will be constructed. For each arm, 250 participants will be sufficient to estimate toxicity to within $\pm 6\%$. Any toxicity occurring with at least 1% probability is likely to be seen at least once (99% probability).

Primary analyses will all be intent-to-treat. We will perform additional analyses per protocol, to understand how variation in treatment in the neoadjuvant arm can impact the analyses.

CLOSED EFFECTIVE 05/05/2022

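### Randomization is balanced on LDH and stage, but neither factor enters the primary log-rank test or the secondary analyses; if they are prognostic, the primary test runs slightly below its nominal 15% level

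*Combined protocol and SAP*

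**What the plan says.** Section 6.0 randomizes patients "in a 1:1 fashion, using dynamic balancing". The two factors are baseline LDH (two levels, split at the institutional upper limit of normal) and "Stage of disease at randomization: IIIB* versus IIIC* versus IIID*/IV", which together form six cells.

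Section 11.2 defines the primary EFS test: "The final analysis will consist of a log-rank test of the null hypothesis at the two-sided 15% level". Its futility look at 51 events consists of "testing the alternative hazard ratio from a Cox regression model at the one-sided 2.5% level". Section 11.4 says that overall survival (OS), local/regional control and disease control will be "compared between arms using log-rank tests and Cox regression models". None of these statements mentions strata, covariates or adjustment, and no other section carries LDH or stage into a comparison of the arms. The re-design in Section 11.3 changes the sample size to 336 eligible patients and leaves the test and its level alone.

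**The concern.** Balancing on a prognostic factor removes part of the chance variation in the treatment contrast. The variance in a plain log-rank statistic takes no account of this, so it is too large and the test rejects a true null less often than its stated level. The design accepts a two-sided 15% error rate in order to reach 81% power with 104 events, so any unused part of that rate is power given away.

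Two further consequences follow. The unstratified hazard ratio is a marginal one, nearer 1 than the ratio within strata, and the plan does not say which will be reported. The plan also never says outright that the test is unstratified. An analyst who stratifies by the randomization factors could claim to be following it, and the two p-values can fall on opposite sides of the threshold.

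The concern is limited: type I error is not inflated, and stratifying does not make the log hazard ratio more precise.

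**Working it through.** **The plan's own figure.** With 104 events, average hazard ratio 0.64, 1:1 allocation and two-sided 15% (critical value 1.44), Schoenfeld's formula gives

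Φ(|ln 0.64| × √(104/4) − 1.44) = Φ(0.446 × 5.10 − 1.44) = Φ(0.836) ≈ 79.8%,

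close to the stated 81%.

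**Inputs from the documents.** EFS follows the mixture-cure model of Section 11.2: 60% cured and a median of 2 years in the others, against 70% and 2.5 years under the alternative. The sample size is 336 (Section 11.3) and the analysis is at the 104th event.

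**Assumptions.** The documents give no prevalence or EFS effect for LDH or stage, and no accrual time for the re-design. Assumed:
- 20% high LDH, and stages 35/45/20%;
- proportional covariate effects, with IIIC taking the square root of the IIID/IV effect, recalibrated so that each arm keeps its marginal cure fraction;
- Pocock-Simon minimization with probability 0.8;
- 3.5 years' accrual and no futility stopping.

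**Main simulation** (40,000 trials per row, standard error about 0.2 points). The stratified test uses the six LDH-by-stage cells.

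| Assumed HR: high LDH / IIID–IV vs IIIB | Size, plain | Size, stratified | Power change from stratifying |
|---|---|---|---|
| 1 / 1 | 15.1% | 15.1% | −0.3 points |
| 1.5 / 1.5 | 14.7% | 15.2% | 0.0 |
| 2 / 2 | 14.1% | 15.2% | +1.2 (77.6 to 78.8%) |
| 2 / 3 | 13.5% | 15.3% | +1.9 (78.2 to 80.1%) |
| 3 / 4 | 12.0% | 15.2% | +4.5 |

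Three other mixes (10–35% high LDH) at 2/2 and 2/3 give a plain size of 13.4–14.2% and power changes of +0.4 to +2.2 points. With 500 patients and 2 years' accrual, size is 14.6 vs 15.2% and power +0.4 points at 2/2; at 3/4 they are 13.1 vs 15.3% and +2.2 points.

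**Second simulation with other assumptions** (336 patients, 10,000 trials per row, standard error about 0.4 points; 25% high LDH; the stage effect is per step).

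| HR: LDH / per stage step | Size, plain vs stratified | Power, plain vs stratified |
|---|---|---|
| 1 / 1 | 15.2 vs 15.0% | 76.8 vs 76.6% |
| 1.5 / 1.3 | 15.0 vs 15.5% | 76.5 vs 76.8% |
| 2 / 1.5 | 13.8 vs 14.8% | 76.3 vs 77.6% |
| 2.5 / 2 | 12.2 vs 14.8% | 75.8 vs 79.9% |

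**Is balancing the cause?** Yes. At 2 / 1.5 with simple randomization in place of minimization, the plain test rejects in 14.8% of null trials rather than 13.8%. The spread of the statistic shows the mechanism: under the null, the standard deviation of the plain log-rank z is 0.971 at 2 / 1.5 and 0.931 at 2.5 / 2, where 1 is required. The implied size is 2 × [1 − Φ(1.44/0.971)] = 13.8% and 2 × [1 − Φ(1.44/0.931)] = 12.2%, matching the table.

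**Hazard ratio.** Under the alternative, stratifying moves the estimate from 0.648 to 0.638 at 2/2 and from 0.646 to 0.614 at 3/4. The standard error of the log hazard ratio does not fall (0.2007 to 0.2025 at 2/2).

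**Is a stage effect plausible?** Section 2.0 reports "an average 5-year OS in Stage III patients of approximately 50" per cent and, for Stage IV, that "20% of patients are alive beyond 4 years or longer after diagnosis". Under constant hazards these are −ln(0.50)/5 = 0.139 and −ln(0.20)/4 = 0.402 per year, a ratio of 2.9. This is OS in all Stage III and IV disease, not EFS in resectable patients.

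**The case against.** The strongest reply is that nothing here is invalid. A plain log-rank test after balanced allocation protects the type I error, the ordinary reading of Section 11.2 is that the test is unstratified, and on that reading no second p-value is on offer. The gain is about one point of power with moderate effects and nothing with weak ones, and the largest figures need a stage effect of 4, above the 2.9 from Section 2.0. That ratio is itself a poor guide, because the trial takes only resectable Stage IV, excludes a history of brain metastases, and combines IIID with IV in one stratum. Stratifying also leaves a thin cell, and a stratified final test would sit beside an unstratified futility look. Finally, this is a trial with visibly different treatment sequences and no described blinding, in which Section 11.5 has the study statistician and study chair monitoring endpoints, so a late change of primary test could itself be informed by data.

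Much of this stands. The issue is efficiency and clarity, not validity; the amount is assumed, and the Section 2.0 ratio shows only that stage can matter. The point about timing limits when the change can be made. None of it favors silence: one sentence settles the reading, and stratifying costs almost nothing if the factors turn out not to matter. Different models at the two looks are acceptable, because the futility rule was calibrated to a marginal hazard ratio.

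**Conclusion.** The point holds as an improvement the plan should make, not as an error that invalidates it. Two things are firm: LDH and stage appear nowhere in the specified comparisons, and a plain log-rank test after balancing on prognostic factors is conservative. The amount depends on assumed effects. With hazard ratios of 2 to 3, the actual size is about 13.5–14% against the nominal 15%, and stratifying recovers about 1 to 2 points of power. With weak or no effects the two tests are practically the same. The larger losses (size near 12%, 4 to 4.5 points of power) need strong effects on both factors. The documents supply no EFS effect for either factor, no LDH or stage mix, and no detail of the balancing algorithm.

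**What to change.** In Section 11.2, state that the primary EFS test is a log-rank test stratified by LDH and stage as recorded at randomization, at two-sided 15%, with a hazard ratio from a Cox model stratified the same way and labeled as within-stratum. In Section 11.4, say the same for OS, disease control and locoregional control. Keep the unstratified versions as sensitivity analyses.

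Add a pooling rule applied to event counts with the arms combined: for example, merge high-LDH IIIC with high-LDH IIID/IV if the smaller cell has fewer than 5 events. The threshold is a convention; what matters is that it is fixed in advance without reference to arm.

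Leave the futility look as an unstratified Cox test against the marginal 0.64. If it is stratified, first recompute the stated 45% and 2% stopping probabilities; at 2/2 they shift by about −1.4 and −0.2 points.

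The decision should be dated and made by people who have not seen EFS by arm. If that is no longer possible, keep the unstratified test as primary, say so explicitly, and report the stratified result as a sensitivity analysis.

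The cost is wording and one rule, since both factors are already collected. About 0.3 points of power are lost if neither factor matters. The thinnest cell, high-LDH IIID/IV, holds about 0.20 × 0.20 × 336 ≈ 13 patients under the assumed mix (3 to 35 across the mixes tried) and adds little information. Pooling to five strata gives size 15.2% and power 78.8% at 2/2, the same as six.

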11.3 Sample size re-design

Because accrual to the study has been slower than anticipated, it is expected that 100% of events may be reached before accrual to the study completes, and so the total sample size of the study will be adjusted as follows.

To account for the slower than anticipated accrual rate, a total of 336 eligible, randomized patients will be accrued. If up to 1.5% of patients are not eligible, up to 342 patients will be registered. With the same assumptions for EFS as in the original design, this design should have the same power as the original design using the same alpha. We expect to reach full events within 6 months of completing accrual.

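### Section 11.3 claims unchanged power and 104 events within 6 months of accrual for 336 patients; the Section 11.2 EFS model gives about 77% power, and 104 events only years later

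*Combined protocol and SAP*

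**What the plan says.** Section 11.2 describes event-free survival (EFS) with an exponential-mixture cure model. In the adjuvant arm "60% participants will be long-term survivors", and "median EFS for participants who are not long-term survivors will be 2 years". The alternative for the neoadjuvant arm is 70% and 2.5 years. With 500 eligible patients, 1:1 allocation and 2 years of accrual, "100% of expected events is 104 events across both arms". The final test is a log-rank test at the two-sided 15% level, expected 1.5 years after accrual, and "The power of this design is 81" per cent. The section also warns that hazards are not proportional and that "average hazard ratios from Cox models are expected to become more null with additional follow-up".

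Section 11.3 responds to slow accrual. For the 500-patient plan, "it is expected that 100% of events may be reached before accrual to the study completes". The sample becomes 336 eligible patients. On power: "With the same assumptions for EFS as in the original design, this design should have the same power as the original design", at the same alpha. On timing: "We expect to reach full events within 6 months of completing accrual". The section gives no new event target, accrual duration, observed event rate or calculation.

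**The concern.** In a cure model the number of patients limits the number of events. With a third fewer patients, the same 104 events must come from a much larger share of those who will ever have one, and that takes longer follow-up. Section 11.2 itself says longer follow-up weakens the average hazard ratio, so 104 events from 336 patients should carry less power than 104 events from 500. The 6-month forecast also looks too early under the same model.

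These two statements are the whole statistical case for the smaller trial. If the final analysis waits for 104 events, it comes years later than forecast and with less power than stated. If it is done near the forecast date, the loss of power is larger. Section 11.3 does not say explicitly which applies, so readers and the monitoring committee cannot tell what the primary comparison can deliver.

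**Working it through.** **Inputs.** From Section 11.2: cure fractions 60% and 70%; medians in the non-cured of 2 and 2.5 years; 1:1 allocation; two-sided alpha 0.15; follow-up of up to 10 years per patient. From Section 11.3: 336 eligible patients, 168 per arm. Assumed, because not stated: uniform accrual over A = 2.5 to 5 years.

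**Formula.** For n patients in an arm with cure fraction c and rate λ = ln 2 / median, expected events F years after accrual ends are

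n(1 − c) × [1 − (e^(−λF) − e^(−λ(A+F))) / (λA)].

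**1. Reproduce the 500-patient design (A = 2, F = 1.5).**
- Control arm: 250 × 0.4 × 0.571 = 57.1 events. Neoadjuvant arm: 250 × 0.3 × 0.494 = 37.0.
- The total is 94.1 under the alternative, and 2 × 57.1 = 114.2 if both arms follow the control curve. The average is 104.2, against the stated 104.
- At F = 0 the totals are 45.3 and 55.7, average 50.5, against the stated 51 for the futility look. The stated counts therefore match the average of the two hypotheses, although the text attaches 104 to the alternative.
- Simulated log-rank power at F = 1.5 is 81.3%, against the stated 81%. The model is the plan's own.

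**2. Event ceiling with 336 patients.** Under the alternative the expected number that can ever occur is 168 × 0.4 + 168 × 0.3 = 117.6. The target of 104 is 104/117.6 = 88% of that.

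**3. Timing with 336 patients.**

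| Accrual A (years, assumed) | Events at 6 months: alternative | Control curve in both arms | Average |
|---|---|---|---|
| 2.5 | 48.2 | 58.8 | 53.5 |
| 3.9 | 59.8 | 72.4 | 66.1 |
| 5 | 67.0 | 80.7 | 73.9 |

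| Accrual A (years, assumed) | Years after accrual to 104 expected events: alternative | Control curve in both arms | Average |
|---|---|---|---|
| 2.5 | 5.7 | 3.1 | 4.1 |
| 3.9 | 5.1 | 2.6 | 3.5 |
| 5 | 4.7 | 2.1 | 3.1 |

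For 104 events to be expected at 6 months, accrual would have to last 10.4 years (control curve) or 23.6 years (alternative).

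Section 11.3 gives its own hint about pace. For 500 patients to reach 104 events before accrual ends, accrual must last at least 4.9 years (control curve) or 7.0 years (alternative). At that pace 336 patients take 336/500 of the time, at least 3.3 to 4.7 years. The expected counts at 6 months are then 55 to 65 (alternative) or 67 to 79 (control curve), still well short of 104.

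**4. Power with 336 patients (simulated log-rank test, two-sided 15%).**
- At 104 events: 77.2% (A = 2.5), 76.8% (A = 3.9), 76.6% (A = 5).
- Cross-check: power = Φ(√(d/4) × |ln HR| − 1.44). The model's average hazard ratio at 104 events with 336 patients is 0.65, so Φ(5.10 × 0.431 − 1.44) = Φ(0.757) = 77.6%. In the 500-patient design at F = 1.5 the average hazard ratio is 0.62.
- By follow-up time for A = 3.9: 69.4% at 1 year, 74.0% at 2, 76.2% at 3, 77.0% at 4, 77.7% at 6, 75.8% at 10. Power does not reach 81% at any follow-up time tried.
- At 6 months after accrual, whatever the event count: 60.0% (A = 2.5), 65.0% (A = 3.9), 68.5% (A = 5).
- With follow-up capped at 10 years per patient, about 15% of trials simulated under the alternative never reach 104 events.

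**The case against.** **Power depends on events.** The usual event-based formula with Section 11.2's stated average hazard ratio of 0.64 gives 79.8% at 104 events for any sample size, so expecting the same power is a recognisable approximation. It assumes the hazard ratio does not change with follow-up, which Section 11.2 expressly denies, so it does not rescue the claim.

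**The forecast may not come from the model.** The clause about unchanged EFS assumptions governs the power sentence, and the 6-month forecast is a separate sentence. It may rest on observed pooled events. Section 10.10 makes this plausible: patients who do not register for adjuvant therapy are given an event at 84 days, as are, with one exception, those without protocol surgery. The smooth cure model has no such early cluster. As an illustration, suppose a fraction p of all patients had such events on top of the model. Then 104 events at 6 months needs p = (104 − 80.7)/(336 − 80.7) = 9% at the low end and (104 − 48.2)/(336 − 48.2) = 19% at the high end. These rates are assumed; the documents give none. This reading stands as a possibility, but under it the EFS assumptions have changed and the power statement loses its basis.

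**Which event convention.** Since 104 reproduces as the average of the two hypotheses, the matching time to 104 events is 3.1 to 4.1 years rather than about 5. That is fair, and it should be reported. It is still years beyond 6 months.

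**Baseline for the power loss.** The 81% refers to 1.5 years after accrual, when about 94 events are expected under the alternative. At exactly 104 events the 500-patient design has about 84%, so the like-for-like loss is larger, about 7 points.

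**The trigger.** Section 11.2 measures information in events and Section 11.3 speaks of full events, so an event trigger is the natural reading. The 60 to 68% power is therefore conditional on a calendar-time analysis.

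**Conclusion.** The concern holds. Under the EFS assumptions that Section 11.3 says it keeps, 336 patients give about 77% power at 104 events: about 4 points below the stated 81%, and about 7 below the 500-patient design at the same event count. The 6-month forecast is not supported by that model. It expects 48 to 67 events then under the alternative (59 to 81 on the control curve), and 104 events 4.7 to 5.7 years after accrual (2.1 to 3.1 on the control curve, 3.1 to 4.1 on the average).

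The timing ranges assume uniform accrual over 2.5 to 5 years, but the conclusion does not turn on that choice, since meeting the forecast would take more than 10 years of accrual even on the control curve. The 104 is carried over from Section 11.2, because Section 11.3 names no other target. The power loss is modest if the trial waits for 104 events. The larger problem is that neither the basis of the forecast nor the rule for timing the final analysis is stated.

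**What to change.** Revise Section 11.3 as follows.

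- State that, under the Section 11.2 assumptions, 336 eligible patients give about 77% power at 104 events. Put the expected time at about 5 years after accrual under the alternative and about 2 to 3 years if both arms follow the control curve. Say which convention the 104 follows, since it reproduces as the average of the two hypotheses (3.1 to 4.1 years on that basis).
- State the accrual duration used and label it as an assumption.
- State whether the event count or calendar time triggers the final analysis, and give the power for that trigger. If it is the event count, add a fallback for the case where 104 events are not reached within the 10-year follow-up limit.
- If the 6-month forecast rests on the observed pooled event rate, remove the claim of unchanged EFS assumptions, report that rate and give the power under it.

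The cost is wording and figures in one section, with no extra patients. The stated power falls by about 4 points and, unless the observed rate supports the forecast, the expected date of an event-driven analysis moves later.
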